10.14.6 Study Exit

A study exit eCRF is required for all subjects. Following study exit, subjects will continue to receive standard medical care. Upon exiting the study, no further study data will be collected, or study visits will occur. All data available through the time of the subject's exit will be used for analysis.

Subjects are urged to remain in the study as long as possible but may be exited from the study for any of the following situations:

- Subject completed study (through Month 12 Follow-up Visit)
- Subject lost to follow-up
- Subject death
- Subject deemed a preoperative screen failure
- Subject deemed an intraoperative screen failure
- Subject did not provide consent or data use protection authorization
- Subject chooses to withdraw (e.g., consent withdrawal)
- Investigator deems withdrawal necessary (e.g., medically justified, failure of subject to maintain adequate study compliance)
- Sponsor request (e.g., study terminated early)

The following information is required to be collected at study exit:

- Reason for exit
- Date of Exit

11. Risks and Benefits

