10.3 Scheduled Follow-up Visit Windows

Data analyses for follow-up visit data will be conducted regardless of whether the visit occurs within the window. A late visit is preferred over an early or missed visit. Should a subject miss a visit or the visit falls outside the prespecified window, a study deviation must be reported, and the original follow-up schedule must be maintained for subsequent visits.

Follow-up visit windows are listed in Table 4 below and are based on the Operative day.

Study Follow-up	Window (days from Operative Day)					
Visit	Window Start / Target	Window End				
Screening	-60	0				
Operative	0	0				
Discharge	0	n/a				
Month 1	30	51				
Month 3	90	120				
Month 12	365	410				

Table 4: Subject Follow-up Visit Windows

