10.14.4 Withdrawal

A subject can withdraw from the study at any time. If the subject wishes to withdraw from the study (i.e., the subject revokes consent), the study site is required to document the reason for exit and the date on the Exit eCRF. In addition, study sites shall follow the regulations set forth by the IRB or EC. Before the subject withdraws consent, an option for follow-up, which does not include direct contact with the subject, should be offered. This may include medical record review or follow-up with Primary Care Provider or referring physician.

If the study investigator voluntarily removes a subject from further study participation, supporting documentation must be in place for the rationale and date of removal. No subjects should be withdrawn by investigator(s) unless compelling medical justification is present. It is recommended investigators discuss with the Medtronic study team prior to withdrawing subjects. Non-study/routine follow-up of withdrawn subjects will be determined by the investigator according to the standard of care at the respective site. Withdrawn subjects will not be replaced.

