10.14.5 Lost to Follow-up (LTFU)

Subject lost to follow-up (LTFU) should be avoided as much as possible, and investigators are urged to do their best to maintain subject follow-up compliance. The site will make every attempt to contact subjects that are noncompliant with study follow-up visits. A subject is considered to be lost to follow-up if the following attempts to contact the subject are unsuccessful:

- Three (3) phone calls should be made to the subject at various times and at least one day apart.
 Each attempt should be clearly documented in the source documents and the response or lack thereof should be captured.
- If there is no response to the phone calls, then an official, certified letter should be written and sent to the subject. A copy of the letter and return or delivery receipts should be retained in the subject's source document.

In case a subject can no longer be found, the monitor shall check the appropriateness of the site's attempts to contact the subject.

The sponsor must be notified, and the study exit eCRF must be completed. The monitor shall check the appropriateness of the site's attempts to contact the subject.

The subject will not be considered lost to follow-up until the end of the study (Month 12 follow-up visit). When subjects are considered lost to follow-up the investigator will make efforts to confirm the vital status/health status of the subject, as described in the informed consent. Lost to Follow-up subjects will not be replaced. At the end of the study, the study exit eCRF will be completed with a status of Lost to Follow-up.

AFFIX (MaxTack [™] Motorized Fixation Device) Clinical Investigation Plan				
MDT23014	Revision	3.0	Page 47 of 97	Medtronic

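### Section 10.14.6 allows investigator withdrawal for poor study compliance, contrary to 10.14.4 and at odds with 10.14.5 and 10.3, and so permits avoidable missing recurrence data

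*Protocol*

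**What the plan says.** Four provisions of the protocol govern a subject who attends badly.

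- **Section 10.14.4 (Withdrawal)**: "No subjects should be withdrawn by investigator(s) unless compelling medical justification is present". The rationale and date must be documented, and prior discussion with the sponsor is recommended. On replacement: "Withdrawn subjects will not be replaced".
- **Section 10.14.5 (Lost to Follow-up)**: "The site will make every attempt to contact subjects that are noncompliant with study follow-up visits". On timing: "The subject will not be considered lost to follow-up until the end of the study (Month 12 follow-up visit").
- **Section 10.3 (Visit Windows)**: "A late visit is preferred over an early or missed visit". Out-of-window data are analysed, and a missed visit leaves the later schedule unchanged.
- **Section 10.14.6 (Study Exit)** lists among the permitted reasons for exit: "Investigator deems withdrawal necessary (e.g., medically justified, failure of subject to maintain adequate study compliance"). On the consequence: "Upon exiting the study, no further study data will be collected, or study visits will occur". On what is kept: "All data available through the time of the subject's exit will be used for analysis".

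Section 14.7 bases the primary analysis on observed data with no imputation. It adds a sensitivity analysis over all possible values of the missing outcomes, for the primary endpoint.

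**The concern.** Section 10.14.6 puts inadequate compliance beside medical justification as a separate example, so it cannot be read as a kind of medical justification. The subjects whom 10.14.5 tells sites to pursue are the ones whom 10.14.6 lets an investigator exit. No section says which rule prevails, so two sites with the same poor attender could act in opposite ways and both cite the protocol.

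The intervention is a single operation. Missed visits are therefore no reason to stop observing whether the hernia recurs. A non-attender who stays in can still be examined late and counted. Once exited, that subject cannot be.

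At stake is recurrence status at Month 3 (primary) and Month 12 (secondary). The missing values would be selected by attendance, which may be related to outcome. The exit decision lies with the investigator, who under Section 5.2.1 also makes the final decision to report a recurrence, in a single-arm study.

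**Working it through.** **1. The same subject under each section.** Take a subject who missed Month 1, has not yet attended for Month 3 and has not withdrawn consent.

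| Section | What happens |
|---|---|
| 10.14.4 | The investigator should not withdraw the subject, as there is no medical ground |
| 10.14.5 | The site keeps trying to make contact; not lost to follow-up before Month 12 |
| 10.3 | A late Month 3 examination is preferred and is analysed; Month 12 stays on schedule |
| 10.14.6 | The investigator may exit the subject for poor compliance; no further visits or data |

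The first three agree and the fourth departs from them. No other section restores the lost outcome. The no-contact follow-up option in 10.14.4 (for example, record review) is described for subjects about to withdraw consent. The follow-up of up to 30 days after exit in Section 12.5 concerns unresolved related adverse events, not new recurrences.

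**2. Do the plan's figures still hold?** Inputs are from Sections 14.4 and 14.6: goal 8.6%, one-sided alpha 0.025, assumed rate 1.0%, 100 evaluable, 9% attrition. The Clopper-Pearson upper limit for x events in n is the 0.975 quantile of Beta(x + 1, n − x).

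- 3/100: 8.52%, below 8.6%. 4/100: 9.93%, above it. The critical count is 3, as stated.
- P(X ≤ 3 | n = 100, p = 0.086) = 0.0235, within 0.025.
- P(X ≤ 3 | n = 100, p = 0.01) = 0.9816, so power is over 90%, as stated.
- 100 / (1 − 0.09) = 109.9, hence 110 enrolled.

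All stated figures reproduce.

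**3. What if exits take the evaluable number below 100?** At 99 subjects, 3 events give an upper limit of 8.601%, so the critical count falls to 2. Power at 1.0% is then 0.9225. At 88 subjects it is 0.9413, again with a critical count of 2. Power remains over 90%.

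**4. What could informative exits do to the primary result?** Suppose 110 are enrolled, 10 are exited before Month 3 and 3 recurrences are seen in the other 100. The goal is met (8.52%). One unseen recurrence among the 10 would make it 4/110, with an upper limit of 9.05%, and the goal would be missed.

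An illustration over a range follows. **The assumptions are not in the protocol**: a true overall rate of 8.6%, all 10 losses being compliance exits, and a recurrence rate r among those exited. The rate in the 100 observed is (0.086 × 110 − 10r) / 100 = (9.46 − 10r) / 100, and the chance of meeting the goal is P(X ≤ 3 | 100, that rate).

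| r among exited | Rate in observed | Chance of wrongly meeting goal |
|---|---|---|
| 5% | 8.96% | 1.8% |
| 8.6% | 8.60% | 2.3% |
| 15% | 7.96% | 3.8% |
| 20% | 7.46% | 5.4% |
| 30% | 6.46% | 10.7% |

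The error exceeds the nominal 2.5% only if poor attenders recur appreciably more often than the rest. The protocol gives no information on that.

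**The case against.** The strongest reply is that this is one parenthetical example in a permissive list, outweighed by the rest of the protocol. Section 10.14.6 itself urges subjects to remain in the study. Section 10.14.4 asks for documentation and recommends speaking to the sponsor first. Missed visits are reportable deviations, and Section 16.10.2.2 makes persistent failure to follow subjects a possible reason for terminating a site. These controls make misuse less likely. They do not remove the ground, and an investigator who relies on it is acting within the protocol's text.

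A second reply is that little is lost. Data up to exit are used, and Section 14.5 counts an earlier recurrence in the secondary recurrence endpoints even without later data. The Section 14.7 sensitivity analysis would show whether the missing subjects could overturn the primary result. This largely stands and limits the concern. That analysis is not the decision rule, however, and it covers only the primary endpoint. The 12-month endpoints have no such check, although under Section 14.8 they are descriptive.

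Three stronger readings are tempting but unsupported:

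- *One exit beyond the attrition allowance breaks the decision rule.* Section 14.1 already ties the rule of 3 or fewer to at least 100 evaluable subjects. It would take an eleventh loss from 110 to fall below 100, and power at 99 is still about 92%. Fewer subjects also make the goal harder to meet, which is the opposite of a favourable bias.
- *Exit wipes out the subject's recurrence, reoperation or surgical site occurrence data.* Only what would have been observed after exit is lost.
- *Investigators will use the clause to remove recurrences.* Nothing in the document shows this. The text permits selective loss but does not establish it.

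**Conclusion.** The contradiction between 10.14.6 and 10.14.4 is real and in the current text, and the compliance ground runs against the retention rules in 10.14.5 and 10.3. Its consequence is avoidable, possibly informative missing recurrence data: at Month 3 and Month 12 if the exit comes before the Month 3 assessment, and at Month 12 only if it comes later.

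The size cannot be derived from the protocol. It depends on how often the ground would be used and on the recurrence rate among those exited, neither of which is given. The table above shows how the result would respond under stated assumptions and is not an estimate. No sample size, power or decision figure in the protocol is wrong because of this. The point deserves correction because the missing data would be of the study's own making and are cheap to prevent.

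**What to change.** In Section 10.14.6, delete inadequate compliance from the examples under investigator withdrawal, so that the entry agrees with 10.14.4. Add a cross-reference there to 10.14.5, stating that subjects who miss visits remain in the study and that their recurrence status is sought at the next possible contact unless consent is withdrawn.

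The cost is one deleted phrase and one sentence, plus removal of the matching option from the exit form if it has one. Sites take on no new work, since 10.14.5 already requires the contact attempts and 10.3 already keeps the later visits on schedule. The added sentence mostly restates those sections. Its purpose is to stop the exit list being read on its own.

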11.1 Potential Risks

Medtronic follows rigorous Quality Assurance and Control procedures throughout the life of a product, from the business analysis phase through development, market release, and post-market surveillance. The risk analysis process for the AFFIX Study, MaxTack[™] Motorized Fixation Device is being performed in accordance with ISO 14971. Overall, the residual risk for the MaxTack[™] Motorized Fixation Device was deemed acceptable.

The potential risks of the MaxTack[™] Motorized Fixation Device have been described in the Instructions for Use (IFU) and are summarized below. As with any device, there is always a risk of a rare or previously unknown side effect developing from the treatment or use of the device. The IFU will be updated should a new risk become identified.

Risks associated with the use of any Tack Fixation devices may include improper tack placement, deployed tacks having insufficient holding force (resulting in tack/mesh migration, adhesions, erosion, recurrence and damaged mesh), excessive tack penetration, tack penetration through great vessels or cardiac

AFFIX (MaxTack [™] Motorized Fixation Device) Clinical Investigation Plan				
MDT23014	Revision	3.0	Page 48 of 97	Medtronic

structures, tack impinging on nerves, and foreign body reaction (resulting in "meshoma" formation, tack hernias, chronic pain, and infection). Risks associated with the MaxTack[™] Motorized Fixation Device include but are not limited to: seroma, fistula, perforation, hernia recurrence, bowel entrapment, strangulated bowel, tissue damage/trauma, cardiac tamponade and/or damage to pericardium, bleeding/hematoma, acute/chronic pain, nerve damage, infection, allergic reactions to the components of the product, burns, environmental contamination, inflammatory reaction, visceral adhesions, vascular injury, visceral injuries, and injuries to operator. Investigators participating in this study are experienced with the known risks related to standard of care for ventral hernia repair procedures. Due to the nature of the procedure and use of multiple products (tacks and mesh), it may be hard to differentiate between risk associated with the tack vs. those associated with the mesh, and / or the procedure. There are no known risks associated with an interaction of the tacks with any concomitant medication.

11.2 Risk Minimization

Medtronic has further minimized the possibility of risks by performing required laboratory and preclinical testing prior to the AFFIX study, implementing quality control measures into production, processes, providing guidelines for subject selection and evaluation, and providing adequate instructions and labeling. Risks are first and foremost mitigated by device design. Additionally, the potential risks associated with the MaxTack[™] Motorized Fixation Device were identified and are mitigated with warnings and cautions described in the IFU. The CIP includes subject eligibility criteria that excludes patients with higher risk such as those that may have a history of an allergic reaction to the components of the device, or those with an infection. Any potential risks associated with this study are further minimized by selecting qualified investigators and training study personnel on the CIP. The IFU and study training will guide investigators on the proper use of the device. Additionally, physicians performing these procedures will likely have experience of using tackers for mesh fixation.

Investigators will be actively involved in the hernia repair procedure involving MaxTack[™] and follow-up of the subjects. Any complications that occur with the use of the study device (either during the procedure or postoperatively) will be assessed by the investigator and reported per the CIP. Risks will be minimized by careful assessment of each subject prior to, during, and after implant of the study device.

11.3 Potential Benefits

The MaxTack[™] Motorized Fixation Device may offer no benefit. The purpose of the MaxTack[™] Motorized Fixation Device is to fixate mesh. The benefit of surgical prosthetic material fixation to soft tissue in hernia repair is to strengthen/reinforce the weakened defect in the abdominal wall. This type of surgical repair minimizes the risk of complications and reduces the risk of recurrence. The mechanical fixation of prosthetic material during hernia repair with device in combination with the prosthetic material may therefore provide the clinical benefit of a low hernia recurrence rate. Additionally, information collected

AFFIX (MaxTac Clinical Investi				
MDT23014	Revision	3.0	Page 49 of 97	Medtronic

from this study may assist in the design of new product(s), therapy(ies), and/or updates to the MaxTack™ Motorized Fixation Device IFU.

11.4 Risk-Benefit Rationale

As described in the IFU for the MaxTack[™] Motorized Fixation Device, a ventral hernia repair procedure involving a tacker involves risk. These complications are associated with both the procedure itself as well as the devices being used. For patients who are candidates for the study, the benefits of using the MaxTack[™] Motorized Fixation Device during their hernia repair procedure may outweigh these risks.

In conclusion, the MaxTack[™] Motorized Fixation Device has been shown to have a favorable benefit-risk profile based on the criteria of the target population and the risks and benefits potentials of the device.

12. Adverse Events and Device Deficiencies

For enrolled subjects, adverse events (AE) and device deficiencies (DD) will be collected from the time of skin incision until the subject exits. If an AE is considered unresolvable by the investigator, it will be documented within the eCRF that the AE remains unresolved or unrecovered at the time of study exit. Initial reporting of AEs or DDs may be done by phone, email, or by completing as much information as possible on the appropriate eCRF. The completed AE or DD eCRF must be submitted to Medtronic as soon as possible.

12.1 Adverse Events

The following AEs are required to be reported in the study after the point of skin incision until the subject exists:

- All AEs related to the MaxTack[™] Motorized Fixation Device, mesh, or study procedure
- All events that lead to death, regardless of relatedness
- Any non-subject adverse event

Reporting of these events to Medtronic will occur on the applicable AE eCRF. Each event must be reported separately. Documented pre-existing conditions are not considered AEs unless the nature or severity of the condition has worsened. Subject deaths are required to be reported. Refer to Section 12.7 for Subject Death collection and reporting requirements.

12.2 Device Deficiency

The device deficiency (DD) definition is provided in Table 5: Adverse Event and Device Deficiency Definitions. DD information will be collected throughout the study and reported to Medtronic. Note that a DD that resulted in an AE to the subject should be captured as an AE only.

AFFIX (MaxTack [™] Motorized Fixation Device) Clinical Investigation Plan				
MDT23014	Revision	3.0	Page 50 of 97	Medtronic

In the event of a DD, the device should be returned to Medtronic for analysis, if possible. Instructions for returning the study device will be provided. Device deficiencies should also be documented in the subject's medical record.

